Methods: This study is a large, simple and pragmatic trial that compares two protocols for CT surveillance of potentially cancerous small lung nodules. The two protocols are both supported by guidelines from professional societies and consistent with current standards of care. Random assignment to intervention groups will occur at the level of the hospital or health system, and clinical champions at each site will work with clinical and operational leaders to implement the assigned protocol for surveillance during the study period. Eligible patients will be enrolled passively at one of 24 hospitals within 14 health care systems, using automated methods for identification, notification, and registration into the study. We plan to enroll approximately 35,200 unique patients over 28 months and follow them for two years to ascertain outcomes. Data will be collected from electronic health records (EHRs), local and statewide cancer registries, and surveys of patient-reported and provider-reported outcomes. All data will be transferred securely to the Data Coordinating Center for analyses using hierarchical models to account for clustering effects and to adjust for residual imbalances between groups. Sensitivity analyses and analyses to identify heterogeneity of treatment effect will be performed.

Patient Outcomes: Based on our extensive clinical experience, engagement with stakeholders, and qualitative research with patients to date, we have identified the following set of clinical and patient-centered outcomes of interest. Most of the outcomes are amenable to collection by reviewing EHRs.

1. Tumor (T) stage >T1a at diagnosis, according to the American Joint Committee on Cancer (AJCC) classification system, 7th edition, equivalently, stage >T1b according to the AJCC 8th edition;
2. TNM stage >T1aN0M0, according to the American Joint Committee on Cancer (AJCC) classification system, 7th edition, equivalently, stage >T1bN0M0 according to the AJCC 8th edition;
3. Timeliness of lung cancer diagnosis;
4. Lung cancer survival, obtained from membership files and state tumor registries;
5. Emotional distress during surveillance period, measured with the Impact of Event Scale-Revised (IES-R);
6. Anxiety, measured with the 6-item State-Trait Anxiety Inventory (STAI-6);
7. General health status;
8. Overall satisfaction with evaluation;
9. Health care resource utilization during the surveillance period;

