Our choice of outcomes was also guided by several months of conversations with clinical, patient and non-patient stakeholders; our knowledge of the literature on clinical outcomes in lung nodule evaluation;^{39,40} and recent studies performed by members of the research team on patient preferences related to diagnostic testing in general⁴¹ and lung nodule evaluation in particular.⁴²⁻⁴⁴ Aim 1 addresses the goal of an optimum surveillance strategy to diagnose cancer as early as possible to maximize the chances for cure; Aim 2 addresses the anxiety and distress that is experienced by patients with a nodule of uncertain cause, as well as the preferences and satisfaction of providers; Aim 3 focuses on avoiding complications and resource utilization, an important outcome for key stakeholders, including health systems and purchasers, as well as for patients, who often bear the inconvenience and co-payment costs of unnecessary testing. Last,

Aim 4 addresses concerns that more intensive surveillance may be associated with worse adherence by ordering physicians and patients.

All study procedures will be developed and overseen by the PIs. An independent Data and Safety Monitoring Board will monitor the study for unanticipated adverse events and safety, and perform interim analyses after 25% and 50% enrollment. The study will be registered at ClinicalTrials.gov. This proposal was developed in close collaboration with all stakeholders, and additional feedback will be sought (and the protocol will be modified as needed) during kick-off activities, including conference calls, webinars and an in-person meeting. All analyses will be planned in advance and specified in the protocol, including sensitivity analyses and analyses to examine heterogeneity of treatment effect (HTE).

Cluster Randomization: Randomization to one of the guideline-based protocols will be performed at the level of the hospital or health system. All patients with small pulmonary nodules within a given hospital or health system will receive the same recommendations for surveillance.

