Random assignment to one of the two intervention groups at the hospital or health system level will be performed using matching^{45,46} and re-randomization⁴⁷ to ensure balance among several potential confounders: the volume of CT imaging performed, the setting type (integrated healthcare system vs. academic), KPSC vs. other institutions; racial and ethnic distribution; percentage of patients who are current, former, vs. never smokers; inclusion of patients with screening-detected nodules; frequency in using PET for patients with nodules 11-15mm; timing of notification letters to participants; and distribution of insurance type. A biostatistician at the Data Coordinating Center will generate the allocation scheme using statistical software developed in R by [name] at Vanderbilt^{45,46}. All participating organizations have agreed to accept random assignment to one of the two groups. While many of the participating

institutions operate more than one hospital, all but one will undergo randomization at the health system level, because their information systems for managing radiology results are centralized, so assigning individual hospitals to different groups would be difficult. The one exception is KPSC, which operates hospitals in 11 distinct medical service areas (MSA); clinical and administrative leaders at this site have agreed to randomization at the level of the MSA. Site PIs, clinical champions, and their multidisciplinary collaborators (including radiologists, primary care physicians, pulmonologists, oncologists and surgeons) will work with key administrative leaders and other clinicians to implement the assigned imaging protocols during the study period. Although randomization is at the hospital level, the unit of analysis will be the individual patient, and we will compare patients randomized to more vs. less frequent surveillance, after adjusting for potential clustering within sites.

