H1a: Among participants with nodules that prove to be cancerous, less intensive surveillance will be non-inferior to more intensive surveillance for: (a) the frequency of cancer progression beyond AJCC 7th edition stage T1a disease (or T1b for AJCC 8th edition) and (b) the frequency of cancer progression beyond AJCC 7th edition TNM stage T1aN0M0 (or T1bN0M0 for AJCC 8th edition). In addition, among participants with *lung nodules*, less intensive surveillance will be non-inferior to more intensive surveillance for: (a) the frequency of cancer progression beyond AJCC 7th edition stage T1a disease (or T1b for AJCC 8th edition); and (b) the frequency of cancer progression beyond AJCC 7th edition TNM stage T1aN0M0 (or T1bN0M0 for AJCC 8th edition).. Furthermore, in exploratory analyses for HTE, we hypothesize that individuals who are most likely to benefit from more intensive surveillance will include older people, people with larger nodules (>8 mm), patients with solid or part-solid nodules (compared with non-solid

nodules), and individuals with nodules detected by screening (compared with individuals who have nodules that are incidentally detected).

H1b: Among participants with nodules that prove to be cancerous, more intensive surveillance will result in more timely diagnosis than less intensive surveillance.

H1c: Among participants with nodules that prove to be cancerous, less intensive surveillance will be non-inferior to more intensive surveillance for overall survival. Among participants with lung nodules, less intensive surveillance will be non-inferior to more intensive surveillance for overall survival.

H2a: Among all participants with a lung nodule ≤ 15 mm, more intensive surveillance will be associated with greater levels of emotional distress and state anxiety at 13-24 months, but levels of distress and anxiety similar to less intensive surveillance at 1-2 months and ≥ 25 months.

H2b: Among all participants with a lung nodule ≤ 15 mm, more intensive surveillance will be associated with scores similar to less intensive surveillance for general health status at 1-2 months, 13-24 months and ≥ 25 months.

H2c: Among participating radiologists and pulmonologists, satisfaction with the surveillance protocol will be greater among those who practice at institutions assigned to the less intensive protocol.

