Patient surveys: To examine whether among all participants with a lung nodule ≤ 15 mm, more intensive surveillance will be associated with greater levels of emotional distress and state anxiety at 13-24 months, but levels of distress and anxiety similar to less intensive surveillance at 1-2 months and ≥ 25 months, comparisons of the levels of emotional distress and state anxiety (measured according to the scoring systems detailed in Table 4) will be assessed at 1-2, 13-24, and ≥ 25 months from the first CT scan, respectively, again using a hierarchical model to capture site-to-site variability. At each time point, we will compare the levels between surveillance groups via a mixed effects model, where site will be considered as random effects to account for within-cluster correlations. Formal tests of both between-site and between-subject heterogeneity will be used to rule out sources of clustering that are not warranted. Structural Equation Models will be used to compare levels of distress and anxiety at 13 months, using second-order factors when valid subscales exist, to assess whether accounting for measurement error in the survey items changes our conclusions. Finally, we will use Latent Class Regression (LCR) to identify subgroups of the study population whose change in levels of emotional distress and state anxiety may differ, since LCR allows for modeling of time trends along with adjustment demographic and clinical characteristics within an arbitrary number of latent classes.⁶² For example, there could be the following three classes: 1) patients whose

levels are elevated at 1-2 months after being notified of a nodule, but then drop off and stay low throughout follow-up; 2) patients whose levels are elevated at 1-2 months and stay high throughout follow-up; 3) and patients whose levels are normal at 1-2 months following surveillance, and then increase during follow-up. The differences in changes of levels of distress and anxiety between the latent classes over time would then be assessed by including a piecewise linear function of time in the LCR model, as described above.

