For H2b, to investigate whether among all participants with a lung nodule ≤ 15 mm, more intensive surveillance will be associated with scores similar to less intensive surveillance for general health status at 1-2 months, 13-24 months, and ≥ 25 months, a mixed effects model, including all subjects who complete at least two sets of surveys and the time variable as a categorical variable, and will allow the parameters corresponding to time trends to be random effects, so as to allow for between-subject heterogeneity in those trends. Formal tests of both between-site and between-subject heterogeneity will be used to rule out sources of clustering that are not warranted. The mixed effects models will be adjusted for potential confounders including age, gender, ethnicity/race, smoking, BMI, nodule size, and any facility-level factors balanced during the randomization. Interaction between the treatment assignment and time will also be considered in the models and subgroup analysis will be conducted at separate time points if the interaction term is significant. For H2c, to examine whether among participating radiologists and pulmonologists, satisfaction with the surveillance protocol will be greater among those who practice at institutions assigned to the less intensive protocol, similar analysis strategy for H2b will be adopted.

Similar methods will be used to evaluate ordering specialist, primary care, and radiologist knowledge attitudes and beliefs about existing guidelines for pulmonary nodule evaluation and provider satisfaction with the surveillance protocol and the evaluation process measured at approximately mid-way during follow-up.

Aim 3: Health care resource utilization and exposure to diagnostic radiation

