adherence indicators and the surveillance arm will be obtained. To examine whether among all participants with a lung nodule ≤ 15 mm, more intensive surveillance will be associated with worse adherence to the surveillance protocol than less intensive surveillance, we will use hierarchical logistic regression that includes random site effects, with and without adjusting for potential confounders including age, gender, ethnicity/race, smoking, BMI, nodule size, and any facility-level factors balanced during the randomization.

Sample size and power calculations by aim

Preliminary data from a retrospective study of patients who underwent one or more chest CT scans at KPSC (2006-2012) showed that 76% of chest CT scans are performed in unique patients, and that approximately 30% of these individuals will have a prior history of cancer. Of the remainder, approximately 32% of unique patients (with no prior cancer diagnosis) who undergo chest CT will have a pulmonary nodule ≤ 30 mm, and 72% of all nodules measure ≤ 15 mm. Thus, we expect that approximately 16% of all unique patients who undergo chest CT will have a qualifying pulmonary nodule measuring ≤ 15 mm and no prior history of cancer. Data provided by participating sites indicates that more than 376,000 chest CT scans will be performed during the planned 20-month enrollment period in over 279,500 unique individuals (**Table 1**). This translates to an estimated target population size of approximately 45,000 patients with qualifying nodules. Allowing for site-level variation in the proportion of patients with a prior history of cancer and patients with nodules detected on prior chest CT scans, we will passively enroll a minimum of 35,200 individuals with a nodule ≤ 15 mm at one of the 14 health systems (24 individual study sites for cluster randomization) during the initial 28-month recruitment period. To allow time to complete the evaluation and accrue outcomes, patients will be followed for at least 2 years during the funding period. Among these individuals with small pulmonary nodules, we assume (based on data from KPSC) that 3.0% will be diagnosed with lung cancer, resulting in a sample size of approximately 1,056 patients with cancerous nodules.

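### The Aim 2 analysis plan lets a heterogeneity test remove the site term from between-arm models, although site is the unit of randomisation

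*Combined protocol and SAP*

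**What the plan says.** The Cluster Randomization section states: "Randomization to one of the guideline-based protocols will be performed at the level of the hospital or health system". It adds "Although randomization is at the hospital level, the unit of analysis will be the individual patient", with adjustment for clustering within sites. The sample size section counts "24 individual study sites for cluster randomization", and the Abstract promises "analyses using hierarchical models to account for clustering effects".

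In the Analysis Plan, H2a compares distress and anxiety between arms separately at each time point in a mixed model where "site will be considered as random effects to account for within-cluster correlations". The next sentence reads: "Formal tests of both between-site and between-subject heterogeneity will be used to rule out sources of clustering that are not warranted". The same sentence appears under H2b (general health status), and H2c borrows the H2b strategy. The plan does not name the test, its level, or the action that follows from its result. Nowhere does it say that the site term stays whatever the test shows.

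By contrast, the hierarchical models for the primary endpoint (H1a) and for resource use (H3a) include random site effects with no test attached.

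**The concern.** When whole sites are allocated to arms, patients at one site share both the arm and whatever else is particular to that site. A non-significant variance test does not show that this shared component is absent. With 24 sites and a small ICC, such a test often misses it. If site is then dropped, patients are treated as independent and the interval for the arm difference is too narrow.

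In H2a each patient contributes one score per model, so between-site clustering is the only clustering the test could remove there. The plan itself assumes site variation for Aim 2, since its power statement uses ICC 0.01.

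Distress and anxiety are the primary Aim 2 endpoints, and H2a predicts that "more intensive surveillance will be associated with greater levels of emotional distress and state anxiety at 13-24 months". A false positive matters most for that comparison. At the other two H2a time points, and in H2b, the plan predicts similarity.

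**Working it through.** **Inputs from the documents.** 35,200 enrolled, 10% loss, 5% response as the lowest rate considered, ICC 0.01, effect 0.22 SD, 24 randomised sites. Respondents: 35,200 × 0.90 × 0.05 = 1,584, or 792 per arm, as the plan states. Per site: 1,584 / 24 = 66.

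**Assumptions not in the documents.** Twelve equal sites per arm; two-sided alpha 0.05 (stated for Aim 1, not for Aim 2); a site test at 5%; normal outcomes; no effect of matching, re-randomisation or covariates.

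**The plan's own figure first.** Design effect = 1 + (66 − 1) × 0.01 = 1.65. SE of the difference = √(2 × 1.65 / 792) = 0.0646 SD. Noncentrality = 0.22 / 0.0646 = 3.41. Power is 92.6% with a normal reference and 90.3% with a t reference on 22 df. The stated power above 90% is reproduced.

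**How often the test misses site variation.** The within-arm F test has 22 and 24 × 65 = 1,560 df, with a 5% critical value of 1.549. The expected mean squares have ratio (0.99 + 66 × 0.01) / 0.99 = 1.667. The chance of a non-significant result is P(F < 1.549 / 1.667 = 0.929) = 44%.

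**Error when site is dropped.** The naive SE is about 1/√1.65 = 0.78 of the true one, or about 22% too small. Type I error is about 2 × P(Z > 1.96 × 0.78) = 12.7%; simulation gives 12.7% to 12.8%.

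**Overall error.** The two-step rule was simulated from the balanced one-way ANOVA distributions under no arm effect: site-level t on 22 df if the test is significant, otherwise a pooled patient-level test. The result is 7.1%. It splits as 0.444 × 12.7% = 5.6% from trials where site is dropped, and 0.556 × 2.6% = 1.4% from trials where it is kept. Error in the kept trials is low because they are the ones with a large observed site variance. If site is always kept on 22 df, the error is 5.0%.

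**Sensitivity (one input changed at a time).**

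| Change | Test-then-drop | Always kept |
|---|---|---|
| Base case | 7.1% | 5.0% |
| Site test at 1% / 10% / 20% | 9.1 / 6.2 / 5.5% | 5.0% |
| Response 10% / 15% / 20% | 5.9 / 5.3 / 5.1% | 5.0% |
| ICC 0.005 / 0.012 / 0.02 | 6.9 / 6.9 / 5.9% | 5.0% |
| Normal (z) reference | 7.6% | 6.0 to 6.3% |
| Site-size CV 0.4 / 0.6 / 0.8 | 7.6 / 8.2 / 8.9% | 5.2 / 5.5 / 5.8% |
| Matching factors explain half the site variance and are adjusted for | 6.9% | 5.0% |
| Matching removes half the site variance from the arm contrast, no adjustment | 4.7% | 3.0% |

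With z tests the pre-test itself adds 7.6 − 6.3 = 1.3 to 7.6 − 6.0 = 1.6 points. The rest of the distance from 5% is a degrees-of-freedom matter. The CV values and the half-variance shares are assumed.

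No figure is given for H2b, because the documents supply no inputs for it.

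**The case against.** **It may be only a diagnostic.** The sentence before the test commits to site as a random effect, and the Abstract and the Cluster Randomization section commit to handling clustering. The test sentence also mentions between-subject heterogeneity, which has no role in a one-score-per-patient model, so it may have been carried over from a repeated-measures plan. The H2b text names no random site effect explicitly, so the point is less direct there. All this makes the intent uncertain. But an analyst who drops site after a non-significant test would be following the text, and nothing in the plan forbids it.

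**The base case is unfavourable on response.** This stands. A 5% response is the plan's floor, not its expectation, and the 5% site-test level is assumed. At 20% response the excess nearly disappears.

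**The allocation was matched and re-randomised.** This also stands. The 7.1% ignores that step. The H2a text lists no covariates, so the unadjusted case (4.7% against 3.0%) cannot be set aside. A reader might infer that Aim 2 will be tested at 7.1%, or at least above 5%. The documents do not support that, because they give neither the test level nor how much site variance the matching removes.

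**The primary outcome is untouched.** Correct: the H1a model has no such test.

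**Conclusion.** The sentence is wrong as written: it allows a significance test to remove the clustering created by the randomisation. This is more than missing detail, because following the text can produce an analysis that ignores the design.

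The size is modest and conditional. At the plan's floor sample and ICC, with equal sites, a 5% site test and no effect of matching, re-randomisation or covariates, type I error for H2a is about 7.1% against 5.0%. It moves towards 5% with better response or a more liberal site test, and rises with a stricter test or unequal sites. With unadjusted matching it can stay below 5%, though it is still higher than if site were always kept. Error above 5% is possible, not established.

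A reader might also infer that keeping site leaves the stated Aim 2 power intact. That holds only for equal sites with no site-level covariates, as set out with the fix.

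**What to change.** Under H2a and H2b, delete the heterogeneity test as a model-selection step and report the site variance and ICC descriptively. State instead: a random site effect is kept in every Aim 2 between-arm model, whatever its estimated size or significance, with small-sample (site-level) degrees of freedom.

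The change is to wording only and needs no further data or patients. If the true site variance is zero, intervals are about 6% wider (2.074 / 1.960 = 1.058).

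Power at 0.22 SD and 5% response should be restated with the change. It is 90.3% on 22 df with equal sites and no site-level covariates. With two site-level covariates (20 df) it is about 89.9%. With assumed site-size CVs of 0.4, 0.6 and 0.8 (gamma sizes, mean 66, 22 df) it is about 89%, 87% and 85%. Either limit the claim of more than 90% to equal sites without site-level covariates, or give the lower figures.

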 - Pneumothorax requiring tube thoracostomy
 - Bleeding (pulmonary hemorrhage)
 - Acute respiratory failure
 - Acute renal failure
 - Allergic reaction to iodinated contrast material requiring hospitalization
 - Acute myocardial infarction
3. Cumulative radiation dose measured by DLP and effective dose

- Including radiation exposure from surveillance and diagnostic imaging following baseline CT scan through 2 years of follow-up (including 24 month exams).

Aim 4: Adherence with the recommended surveillance protocol

1. Radiologist adherence to assigned protocol
2. Physician adherence to ordering test
3. Patient adherence
 - a. Adherence to first recommended surveillance exam
 - b. Adherence to full protocol

Secondary endpoints:

Aim 1:

1. Proportion of lung cancers that are greater than 20mm, N0, MO
 - Measured as progression beyond AJCC 7th edition TNM stage of T1aN0M0 or AJCC 8th edition stage of T1bN0M)
2. Timeliness of lung cancer diagnosis
 - Measured as time from date of index CT scan to confirmed lung cancer diagnosis, defined as histologic confirmation via pathology, among individuals diagnosed with lung cancer.
3. Timeliness of lung cancer treatment
 - Measured as time from date of index CT scan to date of first treatment including surgery, radiotherapy or chemotherapy, among individuals diagnosed with lung cancer. If a patient receives no treatment, we will censor at end follow-up.
4. Overall survival of patients who prove to have a cancerous nodule,
 - Measured from date of index CT scan to death or censoring among individuals diagnosed with lung cancer.

Aim 2:

1. Patient general health status measured at 1-2 months, 13-24 months, and ≥ 25 months after nodule identification
2. Patient satisfaction with the evaluation process measured at 13-24 months and ≥ 25 months after nodule identification
3. Ordering specialist, primary care, and radiologist knowledge attitudes and beliefs about existing guidelines for pulmonary nodule evaluation measured at baseline
4. Provider satisfaction with the surveillance protocol and the evaluation process measured during the follow-up period

Aim 4: Adherence to use of low radiation-dose techniques

Hypotheses:

We specify the following hypotheses by aim:

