We will continue recruitment through the end of the study to collect additional data for HTE analyses with greater statistical power for Aim 1. We assume 10% loss to follow-up before final diagnosis is established based on KPSC membership data. This yields an estimated sample size for analyses of 960 individuals with cancerous nodules for Aim 1, and 32,000 individuals with small nodules for Aims 2-4.

Aim 1: For the primary outcome, the baseline risk of progression has not been reported. Conservatively, we assume that 5% of patients will progress from a tumor ≤ 15 mm to a tumor > 20 mm during the surveillance period. Assuming a two-sided alpha of 0.05, and an intraclass correlation coefficient (ICC) of 0.01, a sample size of 888 unique patients with cancerous lung nodules (444 per arm) is required to achieve 83% power to detect an absolute increase in tumor progression of 5 percentage points. Thus, our anticipated sample size of 960 unique patients with cancerous lung nodules provides adequate power to show non-inferiority of the less intensive surveillance strategy for our primary outcome of lung cancer stage $> T1a$ at diagnosis. The most uncertainty in our assumptions is for the ICC. We will have at least 80% power to detect a 5% increase in our primary outcome for ICC values of 0.012 or less. At the baseline ICC value of 0.01, a total sample size of 32,560 enrolled (including 888 patients with cancerous nodules) will have 0.83 power; for an ICC value of 0.012, a total sample size of 35,200 enrolled (960 patients with cancer) will also have 0.83 power.

Aim 2: Prior studies of anxiety and distress in lung cancer screening have shown that the identification of a lung nodule leads to anxiety and emotional distress that subsequently dissipates over 1-2 years.^{56 63 52} For our analyses of anxiety and emotional distress, we will have $> 90\%$ power to detect an effect size of 0.22 standard deviation, assuming an ICC of 0.01, even if the response rate is as low as 5%, resulting in an estimated sample size of approximately 792 respondents in each arm.

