Prospective subjects will be enrolled passively from all participating institutions and their network sites. The institutional PI will be responsible for overseeing the study to its completion and that all local, state and federal guidelines for the conduct of human subject research are followed. [name] and the research leadership team are ultimately responsible for the successful execution and completion of this study. Real time study monitoring will be performed to ensure accrual goals are met, patient safety is maintained, and data are collected in a timely manner and are of high quality. The research leadership committee will conduct training for the local study coordinator and site PI. The research leadership team will be available to address questions or concerns as they arise. Monthly communications will provide all sites with timely updates and information.

Sources of Materials

As specified in the protocol, the EHR will be accessed to search existing records for variables and outcomes of interest (e.g. demographics, smoking status, cancer history, radiology and pathology reports). Identifiers (name, gender, address, date of birth, and/or Social Security number) will be used for linking with local and state cancer registries to ascertain tumor size and stage in the patients with nodules that prove to be cancer. Patient-reported outcomes will be collected using validated instruments via the Internet or regular mail at 1-2 months, 13 months and 25 months after the date of the index CT scan. Other than completing these questionnaires, no special study visits, procedures or assessments will be performed. Selected physicians at each institution will be asked to participate in a survey to assess their satisfaction with the assigned protocol for surveillance. Data transfer agreements will be in place prior to all data transfers.

Subjects' privacy will be respected at all times, and all procedures will be HIPAA-compliant. All data will remain confidential and only people who are involved in the study will have access to private information. No information identifying individual study subjects will be released except as required by law. Subjects will be tracked in a local database system and only de-identified data will be sent to the central database at the Data Coordinating Center for analysis. Only certified staff will have access to the database, which will be securely password-protected in a REDCap database.

Potential Risks

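### The H2b general health status model admits only patients with two or more completed surveys, although H2b concerns all participants at each of three windows

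*Combined protocol and SAP*

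**What the plan says.** The Hypotheses section puts H2b in terms of all participants with a nodule ≤15 mm and predicts "scores similar to less intensive surveillance for general health status at 1-2 months, 13-24 months and ≥ 25 months". The Aim 2 secondary endpoints list the measure at the same three windows.

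The only analysis described for H2b is a mixed effects model "including all subjects who complete at least two sets of surveys and the time variable as a categorical variable", with random time trends and covariate adjustment. Arms are compared at separate time points only if the arm-by-time interaction is significant. No reason is given for the two-survey condition, and no version using all respondents is planned.

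For H2a the Analysis Plan says: "At each time point, we will compare the levels between surveillance groups via a mixed effects model". There is no minimum number of surveys.

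The Missing Data section covers variables not captured in the EHR and patients who disenrol. It specifies multiple imputation and a comparison of patients with and without missing data. Its only named sensitivity analysis concerns capture of lung cancers. Survey non-response and death between rounds are not mentioned.

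H2c, on provider satisfaction, is to follow a similar strategy to H2b.

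**The concern.** Under the rule, a patient's answer at 1-2 months counts only if the same patient returns another survey at a later round. The 1-2 month comparison therefore depends on what happens afterwards. Someone who answers only round 2 or only round 3 is also lost.

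What happens between rounds is not the same in the two arms. In Tables 2 and 3 a small solid incidental nodule (below 6 mm) is scheduled for at least one CT in Group A. In Group B it is scheduled for none, with one optional at 12 months. Contact with the health system, and possibly willingness to answer a nodule survey, can differ for that reason. Randomisation does not protect a comparison among people chosen by their later response.

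At stake are the validity of a secondary patient-reported comparison, its precision, and its consistency with H2a. As written, two outcomes from the same survey would be reported in different populations.

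**Working it through.** **1. The plan's own Aim 2 figure.** The power section states more than 90% power for 0.22 SD at ICC 0.01, "even if the response rate is as low as 5%, resulting in an estimated sample size of approximately 792 respondents in each arm". That figure is for anxiety and distress; none is given for general health status.

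- Respondents per arm: 35,200 × 0.90 × 0.05 / 2 = 792.
- Clusters: 13 systems plus 11 KPSC service areas = 24, taken as 12 per arm (assumption). Cluster size: 792 / 12 = 66.
- Design effect: 1 + (66 − 1) × 0.01 = 1.65. Effective n: 792 / 1.65 = 480 per arm.
- Power at two-sided alpha 0.05 (stated for Aim 1, assumed here): Φ(0.22 × √(480/2) − 1.96) = Φ(1.45) = 0.926. With a t reference on 22 df it is 0.903.

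Both agree with the plan. Seven clusters per arm would give 0.852, which does not, so 24 clusters is the reading used.

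**2. Cost in precision.** The documents give no share of respondents who complete two or more rounds. The same formula, with cluster size reduced in proportion, gives for a single-window comparison:

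| Assumed share of 792 kept | n per arm | Power for 0.22 SD |
|---|---|---|
| 100% | 792 | 0.926 |
| 90% | 713 | 0.910 |
| 80% | 634 | 0.888 |
| 70% | 554 | 0.860 |
| 60% | 475 | 0.821 |
| 50% | 396 | 0.769 |

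At 85% kept: n = 673, design effect 1 + (56.1 − 1) × 0.01 = 1.551, effective n = 434, and power = Φ(0.22 × √217 − 1.96) = Φ(1.28) = 0.90. The crossing point is therefore at about 15% excluded.

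**3. Bias, by illustration only.** A simulation was run with 400,000 patients per arm, three rounds, no true arm difference, and assumed correlations of 0.5 to 0.6 between rounds. Everyone answers round 1. The chance of answering the next round depends on the last score, and nobody returns after a missed round. Scores are in SD units, and the true round-1 mean is 0.

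| Assumed drop-out | Share kept, by arm | False arm difference at rounds 1, 2, 3 with the two-survey rule |
|---|---|---|
| Same in both arms | 59%, 59% | 0.00, 0.00, 0.00 |
| Link with health differs by arm | 59%, 60% | 0.17, 0.11, 0.09 |
| Rate differs by arm | 50%, 67% | 0.115, 0.071, 0.055 |
| Unrelated to health | 60%, 60% | 0.00, 0.00, 0.01 |

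In the first row the round-1 level is still too high by 0.29 SD in each arm. A likelihood analysis of everyone with at least one survey kept the arm difference within 0.01 SD in all four cases. The drop-out was built to depend only on observed scores, which is the condition under which that analysis works.

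**4. H2c timing.** The sections do not agree on when providers are surveyed.

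- The Aim 2 secondary endpoints have: "Provider satisfaction with the surveillance protocol and the evaluation process measured during the follow-up period". Table 4 also gives the follow-up period.
- The Aim 2 outcomes section describes a provider satisfaction survey sent at the start of the trial and again near the end of enrolment.
- The Analysis Plan places satisfaction about mid-way through follow-up.

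If satisfaction is measured once, a two-survey condition cannot apply to it.

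**The case against.** The best defence is that the model has random time trends, and a patient with one survey says nothing about an individual trend. The plan does not give this reason, and it would not be enough. Patients with two or more surveys identify the trend variation, while those with one still inform the arm means at their window.

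It can also be said that the endpoint is one item and secondary, that multiple imputation is planned, and that first-round non-response may be the larger selection. The first and third points stand and limit the importance of the concern. The second helps only in part, because the imputation text does not name survey non-response.

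A reader might infer more than the documents support:

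- **That the rule favours the hypothesised similarity.** An equal shift towards better health in both arms moves the levels and leaves the difference alone. Unequal selection would create a difference, of unknown sign.
- **That patients with cancer or worsening illness are removed.** They are removed only if they lack two completed surveys. Nothing in the documents stops surveys at diagnosis.
- **That the retained sample can be bounded.** With independent responses at 5% per round, 3 × 0.05² × 0.95 + 0.05³ = 0.725% complete two or more, about 115 of 15,840 per arm. But 5% is a stress value, independence within a person is implausible, and the count runs over all rounds. On the same assumption only 1 − 0.95² = 9.75% of the 792 round-1 respondents, about 77, would stay in that window. Neither number is a usable bound.
- **That surveys are always a year apart.** The ethics section has them "via the Internet or regular mail at 1-2 months, 13 months and 25 months after the date of the index CT scan", but under the 13-24 and ≥25 month windows rounds 2 and 3 could fall much closer together.

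**Conclusion.** The concern holds. The only H2b analysis described is confined to patients with at least two surveys, which does not match the hypothesis, differs from H2a without explanation, and selects on a post-randomisation event. Levels are distorted if response depends on health. The arm comparison is biased, in an unknown direction, only if that selection differs by arm. Precision is lost in every case where some respondents have a single survey.

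The size cannot be stated from the documents. The power figures rest on assumed shares kept, 12 clusters per arm and two-sided alpha 0.05, and they borrow the anxiety and distress calculation. The simulation shows the mechanism and does not predict this trial's bias. The rule should be changed, but no primary conclusion depends on it.

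**What to change.** In the H2b paragraph of the Analysis Plan:

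1. Replace the two-survey condition with *all subjects who complete at least one survey*, in a likelihood-based mixed model with categorical time, arm-by-time terms and site effects.
2. Report the arm difference with its confidence interval at each of the three windows, whatever the interaction test shows.
3. State how deaths between rounds are handled. Without a rule, the model implicitly treats scores after death as missing at random.
4. Add a sensitivity analysis for survey non-response.
5. Keep the two-or-more-survey set as supportive only.

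For H2c, first reconcile the survey timing across Table 4, the Aim 2 outcomes section, the secondary endpoints and the Analysis Plan. Then name the model, and do not carry the two-survey rule over.

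The cost is a few lines of wording and some extra analysis, with no new data. There is a small downside: the result relies on a missing-at-random assumption, and first-round non-response remains, so even the revised analysis does not describe all participants. If results by arm have already been seen, the change should be labelled as made afterwards and both analyses shown.
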